7.9.2.3.2 Mean of Sensor glucose Values and GMI

Mean number of sensor glucose (SG) in mg/dL and GMI will be analyzed and reported. The mean SG and GMI for a subject at period j will be calculated as the overall mean of the SG and GMI values.

7.9.2.3.3 Standard Deviation (SD) and Coefficient of Variation of Sensor Glucose Values (CV)

The standard deviation (SD) and coefficient of variation of sensor glucose values (CV) will be analyzed and reported. The CV for subject i at period j will be calculated as:

$$\frac{\text{standard deviation of sensor glucose values for subject i at period j}}{\text{mean of sensor glucose values for subject i at period j}}$$

The mean of sensor glucose values for subject i at period j will be calculated as described in section 7.9.1.2.3. The standard deviation of sensor glucose values for subject i at period j will be the standard deviation of all sensor readings during period j.

7.9.2.3.4 Amplitude of Glycemic Excursions (MAGE)

The excursion amplitudes of the glucose values measured by mean amplitude of glycemic excursions (MAGE) will be calculated for two periods using the 6 months sensor glucose data. Analysis will be performed and reported.

7.9.2.3.5 Percentage of Time Spent in Auto Mode and in Manual Mode

The percentage of time spent in auto mode and manual mode for subjects in the continuation phase will be calculated as:

$$\frac{\text{time spent in auto/manual mode}}{\text{total time in AHCL therapy}} \times 100\%$$

Descriptive statistics for the percentage of time in auto mode and manual mode.

7.9.2.3.6 Percentage of Sensor Use for Continuation Phase

Descriptive statistics for the percentage of sensor use during the 6 months (After visit 9 to visit 13) continuation phase will be reported.

7.9.2.3.7 Change in Weight and BMI

The change in weight and BMI from 6 month (Visit 8) to end of 12 months continuation phase (Visit 13) will be calculated, analyzed and reported.

7.9.2.3.8 Change in Total Daily Insulin Dose

The change in total daily insulin dose from end of study phase to end of continuation phase will be computed, analyzed and reported. The total daily insulin dose will be based on pump data uploaded in CareLink Clinical in both study and continuation phase.

7.9.2.3.9 Mean number of SMBG

The mean number of self-monitored blood glucose (SMBG) readings and mean of SMBG values will be calculated in study period and continuation phase from the pump data uploaded in CareLink Clinical and will be reported using summary statistics for quantitative variables.

7.9.2.3.10 Lost days from school or work

Summary number of lost days from school or work will be reported during study phase and continuation phase.

7.9.2.3.11 Questionnaires' scores

The Hypoglycemia Fear Survey (HFS) score, Diabetes Treatment Satisfaction Questionnaire (status version, DTSQs and change version DTSQc) scores and Diabetes Quality of Life Questionnaire (DQoL) will be calculated in each study arm and reported using descriptive statistics for quantitative variables.

Hypoglycemia Fear Survey (HFS)

Hypoglycemia can lead to various aversive symptomatic, affective, cognitive, physiological, and social consequences, which in turn can lead to the development of possible phobic avoidance behaviors associated with hypoglycemia. The hypoglycemia fear survey (HFS) is a psychometric instrument designed

to quantify this fear. The instrument has internal consistency and test-retest stability and varies with elevated glycosylated hemoglobin. The HFS has in most translations two subscales, the behavior subscale

and the worry subscale and has a recollection period of 6 months.

The two subscales of the HFS are scored as: behavior subscale (first 15 items) items are added together,

the 18 Worry subscale items are added together. Additionally, a total score, adding all 33 items, will be computed.

Descriptive statistics for the HFS score (behavior, worry and total) will be reported for Visit 2(baseline), visit 8 (end of 6 months) and visit 13 (end of 12 months).

DTSQs and DTSQc

The Diabetes Treatment Satisfaction Questionnaire (DTSQ) has been specifically designed to measure satisfaction with diabetes treatment regimens in people with diabetes. The DTSQ [status version (DTSQs)]

is an eight-item questionnaire, in which six questions (items 1, 4, 5, 6, 7 and 8) assess treatment satisfaction and the other two assess perceived frequency of hyper- and hypoglycemia.

Each item is scored from 6 (very satisfied) to 0 (very dissatisfied) such that the Treatment Satisfaction score can range from 36 (very satisfied) to 0 (very dissatisfied) and the perceived frequency of hyper- and

hypoglycemia scores range from 6 (most of the time) to 0 (none of the time).

Although the DTSQs has proved highly sensitive to change, in many studies where patients are very satisfied with treatment used at baseline, the DTSQs cannot show improvements when they switch to a new treatment, even though they might be even more satisfied with the new treatment. To overcome the limitation of the DTSQs, a change version (DTSQc) has also been developed, which asks participants to rate how their current treatment compared with their previous treatment.

The DTSQc instrument contains the same 8 items as the DTSQs version. The difference lies in the wording

of the response options and instructions, which, in the DTSQc, direct the respondent to compare their experience of treatment before the study began. All items are rated from +3 to -3.

The DTSQc instructions and response options differ from those of the DTSQs to produce measures of relative change in satisfaction rather than measures of absolute satisfaction:

Treatment satisfaction (change): items 1, 4, 5, 6, 7 and 8 are summed to produce a Treatment Satisfaction

(change) score (range: +18 to -18). The higher the score, the greater the improvement in satisfaction with

treatment; the lower the score, the greater the deterioration in satisfaction with treatment. A score of 0 represents no change.

A major advantage of the DTSQs and DTSQc is that they have been developed to be suitable for people with type 1 or type 2 diabetes using a wide range of treatments, including various methods of insulin delivery, oral medications and diet alone, and is, therefore, appropriate for use before and after patients switch between very different treatment regimens.

Descriptive statistics for DTSQs will be reported for Visit 2(baseline), visit 8 (end of 6 months) and visit 13 (end of 12 months).

Diabetes Quality of Life Questionnaire (DQoL)

DQoL has been widely used to measure quality of life among diabetes patients. The instrument has four scales: satisfaction with treatment, impact of treatment, worries about future effects of diabetes, and worries about social and vocational issues. The instrument also includes a generic health item that does not contribute to the scales. A score will be obtained for each dimension. A higher score represents higher quality of life. Descriptive statistics for the DQoL score will be reported for Visit 2(baseline), visit 8 (end of 6 months) and visit 13 (end of 12 months).

7.10 Safety Evaluation

7.10.1 Number of severe hypoglycemic events

Severe Hypoglycemia is an event requiring assistance of another person due to altered consciousness to actively administer carbohydrate, glucagon, or other resuscitative actions. This means that the subject was impaired cognitively to the point that he/she was unable to treat him or her self, was unable to verbalize his or her needs, and was incoherent, disoriented and/or combative. These episodes may be associated with sufficient neuroglycopenia to induce seizure or coma. Plasma glucose measurements may not be available during such an event, but neurological recovery attributable to the restoration of plasma glucose to normal is considered sufficient evidence that the event was induced by a low plasma glucose concentration. Total number of severe hypoglycemic events reported in the eCRF, during Continuation Phase will be reported. Total number of severe hypoglycemic events during the Continuation Phase (from date of Visit 9 to date of Visit 13) will be reported by treatment arm. The number of severe hypoglycemic events per year will be computed for each subject based on the entire continuation phase duration (happening after Visit 10 to and including Visit 13). If a subject i is followed up for x_i years and the number of observed severe hypoglycemic events during that follow up is m_i , the number of severe hypoglycemic events per year (SHEyear) for patient i will be estimated as:

$$\frac{m_i}{x_i}$$

Annualized crude incidence rates will be expressed as number of severe hypoglycemic events per 100 patients' year and will be calculated as:

$$\frac{\sum_{i=1}^n m_i}{\sum_{i=1}^n x_i} \times 100$$

where $i=1, 2, \dots, n$ and n total number of subjects.

The number of severe hypoglycemic events per 100 patients' year during the study phase will be reported by study arm.

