7.1.3.3 Safety set

Safety analysis will include all subjects entered continuation phase and safety data will be presented. Any AE and SAE occurring after the date of visit 9 to the date of Visit 13 will be reported as happening in the continuation phase and will be reported according to the randomization arm that the subject was assigned. For comparison of safety in the two periods, the safety set is composed of all subjects in study period and continuation phase and assessed and analyzed as members of each period.

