7.2 General Methodology

The data from control group and treatment group will be evaluated independently for all endpoints. Also, Cohort A and Cohort B will be analysed independently.

Summary statistics for Continuous variables will be represented by number of subjects(n), mean, median, standard deviation, minimum and maximum and categorical variables will be represented by counts and percentages. P-values for hypothesis testing will be evaluated based on two-sided testing using significance level of 0.05. Confidence intervals will be reported as two-sided 95% confidence intervals. For comparison of primary, secondary, and ancillary endpoints, normality will be verified for appropriate statistical methodology. Comparisons between the study phase and the continuation phase will be performed using a paired T-test for testing the statistical significance of the difference in continuous variables if normality assumption is met or Wilcoxon signed rank test in continuous variables if normality assumption is not met.

The templates for Tables, Listings and Figures (TLFs) will be available in the TLFs document.

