7.9.1.3.6 Percentage of Sensor Use for Continuation Phase

Descriptive statistics for the percentage of sensor use during the 6 months (After visit 9 to visit 13) continuation phase will be reported.

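### SAP 7.10.1 counts severe hypoglycaemia from Visit 9 but bases the annualised rate on time after Visit 10, and the 7.10.3 count sentence does not name the continuation phase

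*SAP*

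**What the plan says.** The SAP covers the continuation phase (section 3.1) and calls all its analyses exploratory (sections 4 and 6).

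Section 7.10.1 gives two windows for severe hypoglycaemia. The total is taken "during the Continuation Phase (from date of Visit 9 to date of Visit 13) will be reported by treatment arm". The per-subject yearly rate is "based on the entire continuation phase duration (happening after Visit 10 to and including Visit 13"). In the rate formula the follow-up time is x_i, and m_i is defined by "the number of observed severe hypoglycemic events during that follow up is" m_i. The section closes by saying that the rate per 100 patient-years "year during the study phase will be reported by study arm". Section 7.10.2 computes the ketoacidosis rate in a similar way. It also attaches that rate to the study phase, but adds that it is reported by periods.

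Elsewhere the phase starts after Visit 9. Section 7.1.3.3 says that any AE or SAE "occurring after the date of visit 9 to the date of Visit 13 will be reported as happening in the continuation phase". Section 7.9.1.3.6 describes sensor use "during the 6 months (After visit 9 to visit 13) continuation phase will be reported", and 7.9.2.3.6 does the same for the treatment group.

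The count sentence in 7.10.3 covers SAEs, SADEs, USADEs, device deficiencies and device deficiencies with SADE potential. It names run-in and study phase, and not the continuation phase.

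**The concern.** A window that opens after Visit 10 is not the entire continuation phase: Protocol 9.4 places Visit 10 inside that phase. Two summaries of one endpoint, in one paragraph, therefore cover different time. An event between Visits 9 and 10 would appear in the table of totals and be missing from the rate, so the two could not be reconciled within an arm.

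The omitted time also differs in kind. Under Protocol 9.3 control subjects start the investigational pump at Visit 9, so they lose their first days on the device. Treatment subjects are already on AHCL and lose a longer stretch of established use.

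The 7.10.3 wording raises a second problem. A programmer who follows it literally would produce no continuation-phase count of serious events or device deficiencies, although that is the phase the SAP exists to analyse and the one that holds the control arm's AHCL exposure.

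**Working it through.** The documents state no rate, event count or precision for this point, so there is no figure to reproduce. The check sizes the interval between Visits 9 and 10 from the visit schedule in Protocol 9.3 and 9.4, with 1 month = 365.25/12 = 30.44 days.

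**Control arm**
- Visit 10 = Visit 9 + 3 days (window ±1 day).
- Visit 13 is reached through 11A (Visit 9 + 7 days), 11C (+7 days), 11E (+1 month), 12 (+1 month) and 13 (+3 months): 14 + 5 × 30.44 = 166.2 days after Visit 9.
- Share omitted = 3/166.2 = 1.8%. Over the Visit 10 window it is 2/166.2 = 1.2% to 4/166.2 = 2.4%.

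**Treatment arm**
- Visit 9 = Visit 8 + 14 days (window +7 days). Visit 10 = Visit 8 + 1 month = Visit 8 + 30.4 days (window ±7 days). Gap = 30.4 − 14 = 16.4 days.
- Visit 13 = Visit 10 + 1 + 1 + 3 months = Visit 10 + 152.2 days, so Visit 9 to Visit 13 = 16.4 + 152.2 = 168.6 days.
- Share omitted = 16.4/168.6 = 9.7%.
- Over the Visit 9 and Visit 10 windows, with Visit 13 timed from the actual Visit 10, it is 2.4/154.6 = 1.6% to 23.4/175.6 = 13.3%. Holding Visit 13 at its nominal date instead gives 1.5% to 13.9%.

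**Effect on a rate.** Assume that 32 subjects per arm enter the phase in Cohort A and all reach Visit 13.
- Control: 32 × 166.2/365.25 = 14.56 patient-years from Visit 9, and 32 × 163.2/365.25 = 14.30 from Visit 10.
- Treatment: 32 × 168.6/365.25 = 14.77 from Visit 9, and 32 × 152.2/365.25 = 13.33 from Visit 10.
- One event after Visit 10 gives 6.9 or 7.0 per 100 patient-years in control and 6.8 or 7.5 in treatment, from Visit 9 and Visit 10 respectively. The choice of window moves it by about 0.1 and 0.7.
- One event between Visits 9 and 10 adds 1 to the count and 0 to the rate as written.

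**Start of the phase.** Sections 7.1.3.3, 7.9.1.3.6 and 7.9.2.3.6, and the count sentence of 7.10.1, all use Visit 9. Only the parenthesis in the rate sentence uses Visit 10. The Visit 9 rules still differ by a day: the 7.10.1 count includes the date of Visit 9, while 7.1.3.3 starts after it. For control subjects that date is the day of pump start.

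**Coverage of 7.10.3.** Section 7.1.3.3 assigns AEs and SAEs to the continuation phase. SADEs and USADEs are adverse events by definition (Protocol 11.2), so that rule reaches them. Device deficiencies that lead to no adverse event are not named there. For them the documents offer general commitments only: inclusion in the study reports (Protocol 11.3.2), descriptive statistics for all safety endpoints (Protocol 13.6), and presentation of safety data for subjects who entered the phase (SAP 7.1.3.3).

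**The case against.** The strongest reply is that this is one stray parenthesis. The words just before it speak of the whole phase, and three other sections point to Visit 9, so a careful programmer would probably choose Visit 9. The analyses are exploratory, and under a constant hazard even the later window gives an unbiased rate. All of that stands. It limits the consequence but does not remove the conflict, because the parenthesis is an explicit rule for the rate.

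Four stronger readings are tempting, and the documents do not support them.

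- A reader might infer that events from Visit 9 are divided by time from Visit 10, which inflates the rate. They are not: m_i is counted over the same follow-up as x_i.
- A reader might infer that the unequal omission (1.8% against 9.7%) distorts a comparison of arms. Section 7.2 says that "The data from control group and treatment group will be evaluated independently for all endpoints", so the effect stays within an arm.
- A reader might infer from the closing sentences of 7.10.1 and 7.10.2 that no continuation-phase rate is planned. Section 7.10.1 does define one for severe hypoglycaemia, and 7.10.2 reports ketoacidosis by periods. The study-phase sentences can be read as the comparator for 7.1.3.3, which states: "For comparison of safety in the two periods, the safety set is composed of all subjects in study period and continuation phase". The labels are incomplete, but the analysis is not missing.
- A reader might infer that continuation-phase device deficiencies will go unreported. The general commitments make that unlikely. What is missing is an explicit count for that phase.

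Finally, a value near 7 per 100 patient-years for one event reflects the size of the arm and is not a measure of this error.

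**Conclusion.** The concern holds as a conflict between stated rules. Followed as written, 7.10.1 gives a count and a rate over different time, and 7.10.3 gives no continuation-phase count. At target dates the rate leaves out 1.8% of the phase in control and 9.7% in treatment. These shares rest on the scheduled visit intervals and a 30.44-day month, and they arise only if the parenthesis is applied literally. The practical effect is a count and a rate that may not reconcile within an arm if an event falls in the gap. No alpha, power, sample size or confirmatory conclusion is touched. It is worth correcting before the analysis because the remedy is specific and nearly free.

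**What to change.** In the rate sentence of 7.10.1, replace the parenthesis that starts after Visit 10 with the Visit 9 to Visit 13 window used for the count. Deleting only the reference to Visit 10 would leave the rate without a start date. Use this one window for the count, m_i and x_i in both arms, and for ketoacidosis in 7.10.2.

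State one rule for events on the date of Visit 9, and reconcile 7.10.1 with 7.1.3.3 accordingly. Simply adopting the 7.1.3.3 start would drop control-arm events on the day of pump start from the count. The rule should assign events after pump start that day in the same way in count and rate.

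In 7.10.3, add the continuation phase to the count sentence, including device deficiencies and those with SADE potential. In the closing rate sentences of 7.10.1 and 7.10.2, name both the study phase and the continuation phase.

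The cost is SAP wording in these sections, with a matching edit to 7.1.3.3 if its start date changes. No new data are needed.

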FLAIR Study	12 weeks, randomized vs 670G, two-sequence crossover multi-center study in 112 subjects 14-30 years old with Type 1 Diabetes in United States, Germany, Slovenia and Israel	Efficacy and Safety, Time in Hyperglycemia >10 mmol/L and Time in Hypoglycemia 3.0 mmol/L	Completed 2020
Medtronic ADAPT study	2 weeks run-in + 6-month randomized phase AHCL vs MDI, single crossover + 6-month continuation AHCL with 124 subjects > 18 years old with Type 1 Diabetes in France, UK and Germany	Efficacy and Safety, HbA1c	Expected completion 2021

This Statistical Analysis Plan (SAP) will be used to support analysis of the continuation phase of the ADAPT study. The Statistical Analysis Plan has been designed to document, before data is analyzed, the planned analyses for the final report. This SAP does not limit the analysis in reports, and additional analyses of the study data beyond this plan might be conducted. However, this document provides the basis for the statistical sections of the final report. Analyses not planned in the SAP and incorporated into the final report will be referred to as “not-prespecified”. Further, in case any analyses will be done differently than planned in the CIP or SAP, an explanation will be provided in the final report.

4. Continuation Phase Objectives

All analysis in this document is exploratory. Cohort A and Cohort B will be analysed independently.

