7.10.2 Number of diabetic ketoacidosis events

A diabetic ketoacidosis event is defined as an event of blood glucose greater than 250 mg/dL(13.9 mmol/L) arterial pH less than 7.3, bicarbonate less than 15mEq/l, moderate ketonuria or ketonemia, and requiring treatment within a health care facility.

Total number of diabetic ketoacidosis events will be reported continuation phase categorized by study arm. The number of diabetic ketoacidosis events per 100 patients' year during the study phase will be calculated in a similar way as in section 7.10.1 and will be reported by periods.

7.10.3 Number of Serious Adverse Events, Serious Adverse Device Effects, Unanticipated Serious Adverse Device Effects and Device Deficiencies

Serious Adverse Event (SAE) is adverse event that led to any of the following:

- a) death,
- b) serious deterioration in the health of the subject, users or other persons as defined by one or more of the following:
 - 1. a life-threatening illness or injury, or
 - 2. a permanent impairment of a body structure or a body function, including chronic disease, or
 - 3. in-patient or prolonged hospitalization, or
 - 4. medical or surgical intervention to prevent life-threatening illness or injury or permanent impairment to a body structure or a body function,
- c) fetal distress, fetal death or a congenital abnormality or birth defect including physical or mental impairment.

NOTE 1: Planned hospitalization for a pre-existing condition, or a procedure required by the CIP, without serious deterioration in health, is not considered a serious adverse event.

For the purpose of this study, the term "life-threatening" in the definition of "serious" refers to an event in which the patient was at risk of death at the time of the event; it does not refer to an event which hypothetically might have caused death if it were more severe.

Serious Adverse Device Effect (SADE) is adverse device effect that has resulted in any of the consequences characteristic of a serious adverse event. Unanticipated Serious Adverse Device Effect (USADE) is serious adverse device effect which by its nature, incidence, severity or outcome has not been identified in the current risk assessment.

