Device deficiency is inadequacy of a medical device with respect to its identity, quality, durability, reliability, usability, safety or performance. It includes malfunctions, use errors, and inadequacy in the information supplied by the manufacturer including labeling. This definition includes device deficiencies related to the investigational medical device or the comparator.

The number of serious adverse events, serious adverse device effects, unanticipated serious adverse device effects, device deficiencies (DD), DD with SADE potential will be reported for run-in and study phase categorized by study arm. The listing of these events will also be reported.

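### SAP 7.10 counts continuation-phase severe hypoglycaemia from Visit 9 but bases the rate on time after Visit 10, and it names the wrong phase for rates and for SADE, USADE and device-deficiency counts

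*SAP*

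**What the plan says.** SAP 3.1 sets the scope: "This Statistical Analysis Plan (SAP) will be used to support analysis of the continuation phase of the ADAPT study".

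Three places define when continuation safety begins:

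- SAP 7.1.3.3 (safety set): "Any AE and SAE occurring after the date of visit 9 to the date of Visit 13 will be reported" as continuation-phase events, by randomised arm.
- SAP 7.10.1, severe hypoglycaemia total: "during the Continuation Phase (from date of Visit 9 to date of Visit 13) will be reported by treatment arm".
- SAP 7.10.1, per-subject yearly rate: "based on the entire continuation phase duration (happening after Visit 10 to and including Visit 13".

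The reporting sentences then name these phases:

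- SAP 7.10.1, severe hypoglycaemia per 100 patient-years: "during the study phase will be reported by study arm".
- SAP 7.10.2, DKA per 100 patient-years: "during the study phase will be calculated in a similar way as in section 7.10.1 and will be reported by periods". The DKA total in the same section is for the continuation phase.
- SAP 7.10.3, SAE, SADE, USADE and device deficiencies: "will be reported for run-in and study phase categorized by study arm".

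**The concern.** Section 7.10.1 calls the time after Visit 10 the whole continuation phase, although the sentence just before it and the safety set both start that phase at Visit 9. Visit 10 also means different things in the two arms. For control subjects it is a training contact shortly after pump start; for treatment subjects it is a telephone call timed from Visit 8. One label therefore removes different amounts of follow-up by arm. In the control arm the time removed is the first days on a pump, before the infusion-set-change training at Visit 10. Protocol 10.1.1 lists infusion-set occlusion leading to DKA among the pump risks.

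The phase names matter for a separate reason. Control subjects use AHCL only from Visit 9 onward. A section that counts SADE, USADE and device deficiencies for run-in and study phase alone plans no such count for the period in which that arm uses the investigational pump. Under Protocol 11.3.2, a deficiency that caused no adverse event goes on its own form, so the AE and SAE commitment in SAP 7.1.3.3 does not pick it up.

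**Working it through.** The SAP states no rate, exposure or precision for safety, so there is no figure to reproduce. The check rebuilds the visit calendar from Protocol 9.3 and 9.4, with one month = 365.25/12 = 30.44 days.

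**Inputs**

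- Visit 9, both arms: Visit 8 + 14 days (window +7). This is pump start in the control arm.
- Visit 10: control, Visit 9 + 3 days (±1); treatment, Visit 8 + 1 month (±7 days).
- Control, later visits: 11A = Visit 9 + 7 days; 11C = 11A + 7 days; 11E = 11C + 1 month; Visit 12 = 11E + 1 month; Visit 13 = Visit 12 + 3 months.
- Treatment, later visits: Visit 11 = Visit 10 + 1 month; Visit 12 = Visit 11 + 1 month; Visit 13 = Visit 12 + 3 months.
- Cohort A: 64 completers of the study phase (SAP 6.1). Assumed here: 32 per arm, all followed to Visit 13.

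**Length of Visit 9 to Visit 13**

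- Control: 7 + 7 + 5 × 30.44 = 166.2 days.
- Treatment: 6 × 30.44 − 14 = 168.6 days.

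**Time between Visit 9 and Visit 10**

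- Control: 3 days (2 to 4 within the window); 3/166.2 = 1.8%.
- Treatment: 30.44 − 14 = 16.4 days; 16.4/168.6 = 9.7%. Within the windows this runs from (30.4 − 7) − 21 = 2.4 days to (30.4 + 7) − 14 = 23.4 days.

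**Patient-years (PY), Cohort A**

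- From Visit 9: control 32 × 166.2/365.25 = 14.56; treatment 32 × 168.6/365.25 = 14.77; total 29.33.
- Left out by starting at Visit 10: control 32 × 3/365.25 = 0.26; treatment 32 × 16.44/365.25 = 1.44; total 1.70, or 5.8% of 29.33. That leaves 27.63.
- The percentages do not depend on the number of subjects, so they hold for Cohort B too.

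**Effect on the reported result**

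- With zero events, the two-sided 95% upper limit is −ln(0.025)/PY = 3.689/PY. For both arms together it is 12.6 per 100 PY from Visit 9 (3.689/29.33) and 13.4 from Visit 10 (3.689/27.63).
- Suppose the only event in an arm falls between Visits 9 and 10. The total reads 1 and the rate reads 0. On one Visit 9 window the rate would be 100/14.56 = 6.87 per 100 PY (control) or 100/14.77 = 6.77 (treatment).

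**Phase named, item by item**

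| Item | Phase in the SAP |
|---|---|
| Severe hypoglycaemia total (7.10.1) | Continuation, from Visit 9 |
| Severe hypoglycaemia per-subject rate (7.10.1) | Continuation, after Visit 10 |
| Severe hypoglycaemia per 100 PY, reporting sentence (7.10.1) | Study phase |
| DKA total (7.10.2) | Continuation |
| DKA per 100 PY (7.10.2) | Study phase, but reported by periods |
| SAE, SADE, USADE, device deficiencies (7.10.3) | Run-in and study phase |
| AE and SAE (7.1.3.3) | Continuation, after Visit 9 |

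The DKA line cannot be followed literally. A study-phase rate cannot start at Visit 10, while a continuation rate that copies the 7.10.1 method would.

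**The case against.** The strongest reply is that these are wording slips with little consequence, and much of it stands.

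- A reader might infer that events counted from Visit 9 are divided by exposure from Visit 10, which would inflate the rate. The SAP does not support that. Section 7.10.1 defines the events in the rate as those observed within the follow-up that forms its denominator.
- A reader might infer that early events disappear. They do not: the severe hypoglycaemia total runs from Visit 9, the DKA total covers the continuation phase, and 7.1.3.3 reports AEs and SAEs after Visit 9. The difference between a start on the Visit 9 date and one after it is a single calendar day, though for control subjects that is the day of pump start. Control subjects also receive pump training at Visit 9, so the omitted days are not untrained days.
- Study-phase rates may be intended. Section 7.1.3.3 foresees a comparison of safety between the two periods, the DKA rate is to be given by periods, and the 7.10.1 formula is built on continuation quantities.
- Device deficiencies are not forgotten altogether. Protocol 11.3.2 promises that all of them will appear in the study reports, and Protocol 13.6 promises descriptive summaries of the safety endpoints.

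A reader might also infer that the plan is deficient for lacking a rate over all AHCL exposure, since "The data from control group and treatment group will be evaluated independently for all endpoints". Neither document calls for such a rate, and the SAP is exploratory and allows further analyses. No study-phase SAP is among the documents, so they cannot show whether one is planned elsewhere. It would be an optional addition, not the correction of an error.

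What remains is that the severe hypoglycaemia rate and count cover different days. The severe hypoglycaemia reporting sentence names only the study phase, and the comparator reading does not explain why 7.10.3 omits continuation counts.

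**Conclusion.** Wrong as written, with a minor numeric effect. The continuation rate in 7.10.1 omits about 3 days per control subject and about 16 days per treatment subject, so it does not describe the same follow-up as the total reported with it. The loss of precision is small. The unequal loss between arms and the omission of the control arm's first pump days are the better reasons to correct it. The phase names in 7.10.1 and 7.10.2 leave the continuation rates without a clear reporting commitment. Section 7.10.3 gives no continuation count of SADE, USADE or device deficiencies, and the general promises elsewhere only partly fill that gap.

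The figures assume target visit dates, 32 subjects per arm in Cohort A and no dropout before Visit 13. The documents give no event rate, so any difference in risk during the omitted days cannot be sized. The confirmatory HbA1c comparison is unaffected.

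**What to change.** 1. In SAP 7.10.1, replace the Visit 10 start of the rate with the Visit 9 start used for the total.
2. Use one Visit 9 to Visit 13 window, for events and exposure alike, in 7.1.3.3, 7.10.1 and 7.10.2, and state whether the Visit 9 date itself is included.
3. Name the continuation phase for the rates per 100 patient-years in 7.10.1 and 7.10.2. If study-phase rates are wanted as a comparator, say so and report the two periods side by side.
4. In 7.10.3, name the continuation phase for every count, including device deficiencies and those with SADE potential.

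The cost is SAP wording only, with no new data. Making the change before analysis also avoids having to justify a departure in the study report, which SAP 7.12 would otherwise require.
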